2.5.2 Handling of intercurrent events

Not applicable.

2.5.3 Handling of missing values not related to intercurrent event

For an NTB outcome at any visit, if more than three out of five NTB items are missing, the total z-score will not be derived and will be set to missing. Completely missing visits will be handled

through the MMRM model, which implicitly imputes missing data under missing at random (MAR) assumption.

2.5.4 Sensitivity analyses

To assess the robustness of the primary analysis results, several sensitivity analyses may be explored, using the primary model adjusted for several important baseline prognostic factors, such as age and educational level.

2.5.5 Supplementary analyses

A supplementary analysis will be performed by averaging the screening and baseline visits to serve as new baseline, the visits at day 57 and Day 85 to serve as new day 85, and the last 2 visits (day 141 and Day 171) to serve as new Day171.

A supplementary analysis may involve estimation of treatment effects and contrasts (anti-inflammatory agent vs. placebo) within subgroups (e.g., MCI or mild AD positive versus negative) if the sample size in the subgroups is sufficient.

2.6 Analysis supporting secondary objectives

Key secondary objectives of EXPLAIN-AD are to determine the safety of each individual agent and to demonstrate how each individual agent affects imaging markers of inflammation in early AD.

Safety and tolerability of each agent will be evaluated via adverse events, laboratory measurements, vital signs, physical examination, ECG findings and suicidality assessment. Details are provided in Section 2.7.

2.6.1 Secondary endpoint(s)

2.6.2 Memory, cognition, executive function, and neuropsychiatric outcomes

Memory

The "memory function" composite score is obtained by averaging the following z-scores from the NTB: RAVLT immediate and delayed scores.

Executive function

The "executive function" composite score is obtained by averaging the following three z-scores from the NTB: Wechsler Memory Scale Digit Span, COWAT, and CFT.

Cognition

The DSST is an attention-demanding component of the Wechsler Adult Intelligence Scale-IV. The DSST score is the number of digits coded correctly in a fixed amount of time, whereby higher scores denote better performance.

The eCognitive assessments will include tests on CCI administered on a tablet. The primary derived metrics of these tests are accuracy (obtained through the number of errors made) and speed (obtained through response time in milliseconds).

The Everyday Cognition (ECog) scale is a validated informant-based measure comprised of 39 items covering six cognitively relevant domains. Each item is scored on a 4-point scale (1=better or no change compared to 10 years earlier, 2=questionable/occasionally worse, 3=consistently a little worse, 4=consistently much worse). An "I don't know" response is also included. The total ECog score is calculated as the sum of all 39 items, and the average score is derived from the mean average of all responses. If the response is "I don't know", then the item is not included in the calculation. The lower total ECog and average ECog scores indicate better performance.

Neuropsychriatric inventory (NPI)

The eNeuropsychiatric At-Home and the NPI-D assessments are study partner reported outcome measures of 12 neuropsychiatric symptoms and the distress associated with these disturbances. The NPI total score is in the range from 0 to 144, with higher values indicating greater disturbance.

Ten behavioral and two neurovegetative domains are included in the NPI:

The 10 behavioral domains are:

- A. Delusions
- B. Hallucinations
- C. Agitation/Aggression
- D. Depression/Dysphoria
- E. Anxiety
- F. Elation/Euphoria
- G. Apathy/Indifference
- H. Disinhibition
- I. Irritability/Lability
- J. Aberrant motor behavior

The 2 neurovegetative domains are:

- K. Sleep and Nighttime Behavior Disorders
- L. Appetite and Eating Disorders

For each domain:

- Frequency is rated as:
 - 1. Rarely less than once per week
 - 2. Sometimes about once per week
 - 3. Often several times per week but less than every day
 - 4. Very often once or more per day
- Severity is rated as:

- 1. Mild produces little distress in the patient
- 2. Moderate more disturbing to the patient but can be redirected by the caregiver
- 3. Severe very disturbing to the patient and difficult to redirect

The total score for each domain is:

• domain score = frequency x severity

Caregiver distress is scored as:

- 0. Not at all
- 1. Minimally (almost no change in work routine)
- 2. Mildly (some change in work routine but little time rebudgeting required)
- 3. Moderately (disrupts work routine, requires time rebudgeting)
- 4. Severely (disruptive, upsetting to staff and other residents, major time infringement)
- 5. Very Severely or Extremely (very disruptive, major source of distress for staff and other residents, requires time usually devoted to other residents or activities)

Thus, for each domain there are four scores:

- Frequency
- Severity
- Total (frequency x severity)
- Caregiver distress

The NPI total score will be calculated by adding the scores of the 12 domain total scores together. The distress score is not included in the total NPI total score.

The total distress score (NPI-D) is calculated by adding together the scores of the 12 individual NPI distress questions.

PET CCI

The PET CCI will be examined at baseline and upon completion of week 12.

Imaging analyses will include, but are not limited to:

- Standard uptake values (SUV), SUV ratio (SUVR) and volume of distribution (Vt) in different brain regions (i.e. occipital lobe, whole brain and cerebral white matter) for each CCI PET scan, and change after canakinumab treatment, compared to baseline
- Summary statistics by dose cohort of the relative change from baseline in % Vt, SUV and SUVR CCI after treatment with canakinumab
- Plot of change from baseline of individuals with arithmetic mean overlaid in Vt, SUV and SUVR

Total target

For biotherapeutic agents, measurement of total target concentrations (the sum of free and drug bound target) is used as a PD marker to evaluate target engagement.

In cohort 1, measurement of total IL-1 β concentrations

CCI

in serum and CSF is used as a PD marker to evaluate CCI

Pharmacodynamic (PD) samples will be obtained and evaluated in all participants, including the placebo group.

Immunogenicity (Anti-ACZ885 Antibodies)

IG samples will be obtained and evaluated in serum of all agent treated participants.

To assess potential immunogenicity, serum samples for determination of anti-canakinumab antibodies will be collected at the timepoints defined in the PK/PD/IG Assessment Schedule.

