#### **12.4.3 Handling of missing values/censoring/discontinuations**

For an NTB outcome at any visit, if more than three out of five NTB items are missing, the total z-score will not be derived and will be set to missing. Completely missing visits will be handled through the MMRM model, which implicitly imputes missing data under missing at random (MAR) assumption.

Commercially Confidential Information

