## 12.5 Analysis of secondary endpoints

### 12.5.1 Efficacy and/or Pharmacodynamic endpoint(s)

#### Memory, cognition, executive function, and neuropsychiatric outcomes

The "memory function" composite score is obtained by averaging the following z-scores from the NTB: RAVLT immediate and delayed scores.

The "executive function" composite score is obtained by averaging the following three z-scores from the NTB: Wechsler Memory Scale Digit Span, COWAT, and CFT.

The DSST is an attention-demanding component of the Wechsler Adult Intelligence Scale-IV. The DSST score is the number of digits coded correctly in a fixed amount of time, whereby higher scores denote better performance.

Commercially Confidential Information

The Everyday Cognition (ECog) scale is a validated informant-based measure comprised of 39 items covering six cognitively relevant domains ([Farias et al 2008](#)). Each item is scored on a 4-point scale (1=better or no change compared to 10 years earlier, 2=questionable/occasionally worse, 3=consistently a little worse, 4=consistently much worse). An "I don't know" response is also included. The total ECog score is calculated as the sum of all 39 items, and the average score is derived from the mean average of all responses. If the response is "I don't know", then the item is not included in the calculation. The lower total ECog and average ECog scores indicate better performance.

The NPI-D and the eNeuropsychiatric At-Home assessment are study partner reported outcome measures of 12 neuropsychiatric symptoms and the distress associated with these disturbances. The NPI-D total score is in the range from 0 to 144, with higher values indicating greater disturbance. The eNeuropsychiatric at-home assessment contains a subset of questions from the NPI-D and is scored similarly.

The memory function composite score, the executive function composite score, the DSST score, the overall eCognitive test scores, the total ECog score **PET CCI**, and the total NPI-D score will be analyzed using the same methodology as for the primary endpoint ([Section 12.4](#)).

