2.6.3 Statistical hypothesis, model, and method of analysis

Memory, cognition, executive function, and neuropsychiatric outcomes

The memory function composite score, the executive function composite score, the DSST score, the overall eCognitive test scores, the total ECog score and the average ECog score, and the total NPI and NPI-D scores will be analyzed using the same model as for the primary endpoint (See Section 2.5).

PET CCI

As only one participant has data available, the PET CCI data will be only listed.

Total CCI

For biotherapeutic agents, total ^{CCI} concentration data will be listed by treatment, participant, and visit/sampling time point. Summary statistics will be provided by treatment and visit/sampling time point.

In cohort 1, concentrations of serum and CSF total Commercially Confidential Information will be given in mass per volume units. Concentrations below the LLOQ will be reported as "zero".

Immunogenicity (Anti-ACZ885 Antibodies)

Summary statistics of the number of positive participants (n, %) will be provided by timepoint.

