2.6.5 Handling of missing values not related to intercurrent event

NA

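### The ECog total counts each 'I don't know' item as zero on the natural reading, and the average that avoids this is not named as the ECog result

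*SAP*

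**What the plan says.** SAP 2.6.2 and Protocol 12.5.1 give the same scoring rule. Each of 39 items is scored 1 to 4, and the study partner may also answer 'I don't know'. For the total: "The total ECog score is calculated as the sum of all 39 items". For the average: "the average score is derived from the mean average of all responses". For an unknown item: "then the item is not included in the calculation". On direction: "The lower total ECog and average ECog scores indicate better performance". Neither document rescales the total for unknown items or sets a minimum number of answered items.

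On which score is analysed, the visible list in Protocol 12.5.1 includes "the DSST score, the overall eCognitive test scores, the total ECog score". Redacted text follows directly, so the list may be incomplete. SAP 2.6.3 applies the primary model to "the total ECog score and the average ECog score" without ranking them. The objectives tables (Protocol Table 2-1, SAP 1.2) name ECog at week 24 as the sole endpoint for function and do not say which score.

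On missing data for secondary endpoints, the SAP section headed "2.6.5 Handling of missing values not related to intercurrent event" contains only NA. The one item-level rule is for the NTB (Protocol 12.4.3, SAP 2.5.3): its total is set to missing when more than three of its five components are absent. For visits, Protocol 12.4.3 says: "Completely missing visits will be handled through the MMRM model, which implicitly imputes missing data under missing at random (MAR) assumption".

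**The concern.** A sum over a varying number of items measures two things at once: how impaired the participant is, and how many questions the partner could answer. Because lower is better and the lowest valid answer is 1, leaving an item out of the sum scores better than any answer the partner could have given.

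The analysis is of change from baseline. A participant whose partner answers more items 'I don't know' at week 24 than at baseline will appear to improve with no change in function, and the reverse pattern will appear as decline. The total and the average can then point in different directions, and no rule says which is the ECog result for the function objective. Reusing the primary model does not help: it deals with scores that are absent, not with a score that is present but built from fewer items.

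**Working it through.** **Inputs.** 39 items, scale 1 to 4, unknown items left out, lower is better (SAP 2.6.2, Protocol 12.5.1). The only ECog figure the documents state is a total range of 39 to 195 (Protocol 4.3).

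**1. The stated range.** 39 × 1 = 39 and 39 × 5 = 195. This reproduces on the five response levels listed in Protocol 4.3. On the 1-to-4 scale used for scoring, the range is 39 × 1 = 39 to 39 × 4 = 156. The steps below use that scale.

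**2. Effect of leaving items out of the sum.** With k unknown items, the total runs from 39 − k to 4 × (39 − k). Each omitted item lowers it by the value that item would have had, so by 1 to 4 points.
- k = 4, every answered item at 1: 35 × 1 = 35, below the valid minimum of 39.
- k = 5: range 34 to 136.

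**3. Comparability between participants.** All 39 items at 2 gives 39 × 2 = 78. Only 26 items answered, all at 3, gives 26 × 3 = 78. The totals are equal, but the averages are 2 and 3.

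**4. Comparability between visits.** Take no unknown items at baseline, five at week 24, and no true change.
- Item mean 2: 39 × 2 = 78 becomes 34 × 2 = 68, an apparent gain of 10 points.
- Item mean 3: 39 × 3 = 117 becomes 34 × 3 = 102, an apparent gain of 15 points.

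In general, observed change = true change − (sum of omitted item values at week 24 − sum of omitted item values at baseline). If the same items are unknown at both visits and their values are stable, the distortion cancels. If the bracketed term has the same mean in both arms, the treatment contrast is not shifted and only variance is added.

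**5. The average.** In both cases of step 4 the average is unchanged (68/34 = 2 and 102/34 = 3), and so is 39 × the average (78 and 117). Multiplying by 39 is a change of units, so a prorated total and the average give the same test. The protection is not complete. Suppose the overall item mean is 2 (sum 78) and five unknown items would truly have been 3. The average becomes (78 − 15)/34 = 63/34 = 1.85 and the prorated total 39 × 63/34 = 72.3, against an unscaled total of 63.

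**6. What cannot be calculated.** The documents give no frequency of 'I don't know' answers and no SD for ECog. The size of the added noise, or of any shift in the contrast, therefore cannot be derived.

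**The case against.** The strongest reply is that the plan largely covers this already. SAP 2.6.3 fits the primary model to the average, which is free of the mechanical lowering, and a prorated total would add no new test. That stands, and it limits the point. What remains is that neither score is designated, the only one visible in the protocol's list is the affected one, and no minimum number of answered items is set.

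The practical effect may also be small. Protocol 5.1 requires a partner with frequent direct contact and asks sites to keep the same partner, which should limit changes in unknown counts. ECog is secondary, carries no power calculation, and the primary endpoint is untouched. These points also stand.

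Two stronger readings are tempting. A reader might infer that the exclusion applies only to the average, so that one unknown item makes the total impossible to form and many totals are lost. The sentence order does not favour this: the exclusion follows a sentence defining both scores and precedes one interpreting both. Any count of lost totals would also need an assumed rate of unknown answers. A reader might also infer that the treatment contrast is biased. That requires the change in unknown items to differ by arm. Participants and investigators are blinded, and the documents give no reason to expect a difference.

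Finally, Protocol 4.3 describes a different response scale and mentions no 'I don't know' option. If that form was administered, the figures change and the issue may not arise. Protocol 12.5.1 and SAP 2.6.2 agree with each other on the 1-to-4 form, so the point is made on that basis.

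**Conclusion.** The point holds as a scoring defect in a secondary endpoint. On the natural reading, the stated rule lowers the ECog total by 1 to 4 points per unknown item, can take it below 39, and makes totals non-comparable when the number of answered items differs. The expected consequence is noise when the set of unknown items changes between visits. Bias between arms is possible in principle but not indicated, and the size of either effect is unknown. With no unknown items there is no effect.

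The average already planned largely protects the function objective, but nothing makes it the ECog result. The conclusion assumes that the 1-to-4 form was the one used and that the redacted words in Protocol 12.5.1 do not settle the choice of score. SAP 2.6.3, which is readable on ECog, does not settle it. The defect is worth correcting because the rule as written produces a wrong score and the remedy is simple.

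**What to change.** - **SAP 2.6.2 and 2.6.3:** designate the average as the ECog result, or compute the total as 39 × the mean of the answered items. The two give the same test.
- **SAP 2.6.5:** replace NA with a minimum number of answered items, chosen by the sponsor, below which the score is set to missing and left to the MMRM.
- **Reporting:** tabulate 'I don't know' counts by arm and visit, so that a reader can see whether the issue arises and whether it differs by arm.
- **Timing:** Protocol 6.4 allows the trial statistician access to the randomization list for interim analyses, so a late choice of score could look selective. Date the decision before any unblinded review of ECog data and record it in SAP section 4. If the unscaled total is kept as a supplementary analysis, state that it is the sum of the answered items.
- **Separate documentation point:** reconcile the scale in Protocol 4.3 (range 39 to 195) with the 4-point scale in Protocol 12.5.1 and SAP 2.6.2 (39 to 156) against the form administered.

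The cost is SAP wording and one added table. No new data are needed, because the average uses the same responses and is already modelled. The downside is small: the average and the prorated total both assume that unknown items resemble answered ones, and can still shift when they do not (step 5 of the working). The minimum-items rule and the counts are there to limit and reveal this.

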2.6.3 Statistical hypothesis, model, and method of analysis

Memory, cognition, executive function, and neuropsychiatric outcomes

The memory function composite score, the executive function composite score, the DSST score, the overall eCognitive test scores, the total ECog score and the average ECog score, and the total NPI and NPI-D scores will be analyzed using the same model as for the primary endpoint (See Section 2.5).

PET CCI

As only one participant has data available, the PET CCI data will be only listed.

Total CCI

For biotherapeutic agents, total ^{CCI} concentration data will be listed by treatment, participant, and visit/sampling time point. Summary statistics will be provided by treatment and visit/sampling time point.

In cohort 1, concentrations of serum and CSF total Commercially Confidential Information will be given in mass per volume units. Concentrations below the LLOQ will be reported as "zero".

Immunogenicity (Anti-ACZ885 Antibodies)

Summary statistics of the number of positive participants (n, %) will be provided by timepoint.

2.6.4 Handling of intercurrent events

NA

2.6.5 Handling of missing values not related to intercurrent event

NA

2.6.6 Sensitivity analyses

Sensitivity analyses may be conducted by adjusting the models to important prognostics factors such as age or educational level.

2.6.7 Supplementary analyses

Supplementary analysis of NTB memory, cognition, executive function, DSST and NPI will be conducted using the primary model, by averaging the screening and baseline visits to serve as new baseline, the visits at day 57 and Day 85 to serve as new day 85, and the last 2 visits (day 141 and Day 171) to serve as new Day171.

At home assessments will have their 2 baseline data-points averaged to serve as baseline; data prior to visit 29 will be averaged to serve as Day 29 and data prior to Day 85 will be averaged to serve as Day 85.

In these analyses averaging 2 visits/timepoints, if one data is missing, the other single data will be used as the average.

2.7 Safety analyses

For all safety analyses, the safety set will be used.

2.7.1 Adverse events (AEs)

All information obtained on adverse events will be displayed by treatment and participant.

The number (and percentage) of participants with treatment emergent adverse events (events started after the first dose of study medication or events present prior to start of study treatment but increased in severity based on preferred term) will be summarized in the following ways:

- by treatment, primary system organ class and preferred term.
- by treatment, primary system organ class, preferred term and maximum severity.

Separate summaries will be provided for study drug related adverse events, death, serious adverse events, other significant adverse events leading to discontinuation.

A participant with multiple adverse events within a primary system organ class is only counted once towards the total of the primary system organ class.

In AE summaries, the primary system organ class will be presented alphabetically and the preferred terms will be sorted within primary SOC in descending frequency. The sort order for the preferred term will be based on their frequency in all participants.

In addition, for EudraCT requirements a summary of (1) Serious AEs and deaths, with number of occurrences and (2) Non-serious AEs, with number of occurrences will be produced (an occurrence is defined as >1 day between start and prior end date of record of same preferred term).

2.7.2 **Deaths**

All deaths will be listed using Safety set and post treatment deaths will be flagged. A separate listing of deaths prior to starting treatment will be provided for all screened participants.

